#### 6.2.2.2. Daily Recording of Solicited Events

For studies **using electronic diaries** for the collection of solicited events, a solicited event will be considered present only when a daily recording of Grade 1 or more is present. To determine the grading, the following rule will be used:

**Table 6 Local solicited AE grading**

Administration Site (Local) reaction	Mild (Grade 1)	Moderate (Grade 2)	Severe (Grade 3)
Pain	Mild: Any pain neither interfering with nor preventing normal everyday activities.	Moderate: Painful when limb is moved and interferes with everyday activities.	Significant pain at rest. Prevents normal everyday activities.
Redness *	25 – 50 mm	51 – 100 mm	>100 mm
Swelling	25 – 50 mm	51 – 100 mm	> 100 mm
Lymphadenopathy**	Present but does not interfere with activity	Interferes with normal activity	Prevents normal activity

\* For redness and swelling, in addition to grading the measured administration site reaction at the greatest single diameter, the measurement should be recorded as a continuous variable.

\*\* Defined as localized axillary, cervical or supraclavicular swelling or tenderness ipsilateral to the administration arm.

**Table 7 Systemic solicited AE grading**

Systemic (General)	Mild (Grade 1)	Moderate (Grade 2)	Severe (Grade 3)
Fever (°C) *	38.0 – 38.4	38.5 – 38.9	>38.9
(°F) *	100.4 – 101.1	101.2 – 102.0	>102.0
Headache	Headache that is easily tolerated	Headache that interferes with normal activity	Headache that prevents normal activity
Fatigue	Fatigue that is easily tolerated	Fatigue that interferes with normal activity	Fatigue that prevents normal activity
Myalgia	Myalgia present but does not interfere with activity	Myalgia that interferes with normal activity	Myalgia that prevents normal activity
Arthralgia	Arthralgia present but does not interfere with activity	Arthralgia that interferes with normal activity	Arthralgia that prevents normal activity
Chills	Chills present but do not interfere with activity	Chills that interfere with normal activity	Severe: chills that prevent normal activity

\* Axillary temperature.

### **6.2.2.3. Unsolicited Adverse Events**

Unsolicited adverse event summaries are including serious adverse events unless specified otherwise.

For the summary of unsolicited adverse events, ongoing solicited events reported as unsolicited AEs will not be counted.

Missing severity, relationship with study intervention, and outcome of unsolicited adverse events will not be replaced and will appear as 'UNKNOWN' when displayed in a statistical output.

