### ***Recording of MAAEs***

For each solicited and unsolicited AE the participant experiences, the participant will be asked if they received medical attention (defined as an unscheduled visit to or from medical personnel for any reason, including emergency room visits). This information will be recorded in the participant's eDiary (for solicited AEs) and in the participant's eCRF as part of normal AE reporting (for unsolicited AEs).

Medical attention received for SAEs/AESIs will have to be reported using the normal AE reporting process in the eCRF.

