##### **4.2.1.1. Solicited AEs**

All solicited events must be recorded into the eDiary by the participant during the first 7 days following administration of the dose of study intervention (Day 1 to Day 7 included), irrespective of occurrence or intensity. Solicited events ongoing after Day 7 will be recorded in the eCRF and followed-up until the event has resolved, subsided, stabilized, disappeared, or until the event is otherwise explained, the participant is lost to follow up, or study is completed. If the collection of solicited AEs was not possible for any reasons via the eDiary and solicited AEs were reported to the investigator by the participant, then it would be possible for them to be reported directly to the site staff and submitted (e.g., via the eCRF).

The following administration site events will be solicited:

- a. Pain
- b. Redness
- c. Swelling
- d. Lymphadenopathy, defined as localized axillary, cervical or supraclavicular swelling or tenderness ipsilateral to the injection arm

The following systemic events will be solicited:

- e. Fever
- f. Chills
- g. Headache
- h. Fatigue

- i. Myalgia
- j. Arthralgia

Note: Participants will be instructed to measure and record the axillary temperature in the evening. If additional temperature measurements are taken at other times of the day, participants will be instructed to record the highest temperature in the eDiary.

Grading or actual temperature/redness and swelling will be captured in the eDiary as per a modified grading of symptoms based on the FDA toxicity grading guidance for industry [FDA, 2007] with Grades 3 and 4 combined and swelling evaluated using the actual measurement only (refer to Section 6.2.2.2). When solicited AE data entered by the participant are missing or incorrect, data collected by study investigator/staff will be used in the summaries if available.

The percentage of participants reporting each individual solicited administration site event (any grade, Grade 1, Grade 2, Grade 3, any grade ongoing at day 7 and medically attended events) and solicited systemic event (any grade, Grade 1, Grade 2, Grade 3, any grade ongoing at day 7 and medically attended events) within the 7-day follow up period (i.e., Day 1-Day 7 post-dosing) will be tabulated for each group.

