The duration of solicited AEs of any grade (see Section 6.2.1.10) will be summarized. The start date is the first day during the 7-day solicitation period with the symptom at grade > 0 while the stop date is the last day with the symptom at grade > 0 in or beyond the solicited period. In addition, the duration for specific grade(s) for each symptom defined as the number of days in the reporting period with grade above or equal to specific grade will be summarized.

Prolonged solicited AEs that continue beyond Day 7 or Day 28 will be identified using a flag in listing of AEs.

The percentage of eDiary days completed in the solicited period will be summarized by group. A day is considered completed in the eDiary if it was entered by the participant or the investigator. The percentage of completed days will be calculated as follows:

$$\text{SumSymp}/(7*\text{NumSymp}*\text{ExpSubj})$$

SumSymp is the sum of the total number of days completed for a specific symptom across all symptoms and exposed subjects. NumSymp is the number of symptoms and ExpSubj is the number of exposed subjects.

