#### **4.2.1.2. Unsolicited AEs with onset within the 28 days follow-up period (day 1-28)**

An AE is any untoward medical occurrence in a clinical study participant, temporally associated with the use of a study intervention, whether or not considered related to the study intervention. An AE can therefore be any unfavorable and unintended sign (including an abnormal laboratory finding), symptom, or disease (new or exacerbated) temporally associated with the use of a study intervention.

The verbatim reports of unsolicited AEs will be reviewed by a qualified person and the signs and symptoms will be coded according to the Medical Dictionary for Regulatory Activities (MedDRA) Dictionary for Adverse Reaction Terminology. Every verbatim term will be matched with the appropriate PT.

A study intervention causally related AE is defined as an AE for which the investigator classifies the possible relationship to study intervention as “Yes”. Investigators will not be required to assess the causality of solicited Aes if the onset is during the solicitation period.

The investigator is obligated to assess the relationship between study intervention and each occurrence of each AE/SAE/. The investigator will use clinical judgment to determine the relationship.

The percentage of participants with any unsolicited Aes within the 28-day follow up period (i.e., Day 1-Day 28) with its exact 95% confidence interval (CI) will be tabulated by group and by MedDRA PT and System Organ Class (SOC). Similar tabulation will be done for Grade 3 unsolicited Aes, for any causally related unsolicited Aes, for Grade 3 causally related unsolicited Aes, for unsolicited Aes resulting in a medically attended visit and for SAE.

A data listing for all unsolicited AEs will be provided by age group (< 65 years,  $\geq$  65 years), dose group and participant number.

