#### **4.2.1.3. MAAEs, SAEs and AESIs with onset after vaccination (day1 up to study end)**

The study will capture the following specific over the full study period: MAAE, SAE and AESIs defined as either :

- Potential immune-mediated disorders (pIMDs),
- Any laboratory-confirmed moderate to severe case of COVID-19,
- Myocarditis and pericarditis and,
- Anaphylaxis or severe hypersensitivity within 24 hours after study intervention administration.

All suspected cases of COVID-19, myocarditis, and pericarditis in study participants will be diagnosed and clinically evaluated, which may require unscheduled study site visits and additional testing based on the investigator’s judgment.

The number and percentage of participants with any event for each MAAE, SAE, AESI In addition, summary will be provided by relationship to study intervention, maximum grade/severity and outcome. The worst-case approach will be applied at participant level for the maximum grade/severity, i.e., a participant will only be counted once as the worst case from all the events experienced by the participant.

The percentage of participants with at least 1 report of SAE (any, related, fatal and fatal related), with at least 1 report of MAAE and with at least 1 report of AESI, respectively,

classified by the MedDRA SOC and PT and reported from Dose 1 up to study end will be tabulated with exact 95% CI.

In the AESI/SAE summaries, a participant with 2 or more Aes within the same SOC or PT level but different relationship will be counted only once in the level using the related incident.

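### A solicited reaction that starts in Days 1-7 and first reaches Grade 3 after Day 7, without medical attention, seriousness or AESI status, is in no incidence-by-severity table

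*SAP*

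**What the plan says.** SAP 4.2.1.1 reports each solicited event by grade, by whether it was ongoing at Day 7, and by medical attendance. The window for all of these rows is stated: "within the 7-day follow up period (i.e., Day 1-Day 7 post-dosing) will be tabulated for each group".

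The same section continues data collection past that window: "Solicited events ongoing after Day 7 will be recorded in the eCRF and followed-up until the event has resolved". The output it names specifically for such events is a listing: "Prolonged solicited AEs that continue beyond Day 7 or Day 28 will be identified using a flag in listing of AEs". It also plans a duration summary by grade, namely "the number of days in the reporting period with grade above or equal to specific grade will be summarized", without defining the reporting period.

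For unsolicited AEs over Days 1-28, SAP 4.2.1.2 plans an overall table and then more of the same kind: "Similar tabulation will be done for Grade 3 unsolicited Aes", with others for related and medically attended events. SAP 6.2.2.3 then limits what enters the unsolicited summary: "ongoing solicited events reported as unsolicited AEs will not be counted".

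For MAAEs, SAEs and AESIs from dosing to study end, SAP 4.2.1.3 states that a "summary will be provided by relationship to study intervention, maximum grade/severity and outcome", taking each participant's worst case.

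**The concern.** The exclusion in SAP 6.2.2.3 has a sound purpose: a reaction already counted as solicited should not be counted again as unsolicited. But the solicited table stops grading at Day 7, so for a reaction that worsens later the exclusion removes the only other general table that would carry its peak grade. No replacement is specified.

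The rules therefore treat near-identical events differently. Fatigue starting on Day 8 and reaching Grade 3 on Day 9 is unsolicited by definition (Protocol 10.3.4) and enters the Grade 3 unsolicited table. Fatigue starting on Day 6 at Grade 1 and reaching Grade 3 on Day 9 does not. Two days' difference in onset decides whether a severe reaction is counted.

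Reactogenicity is part of a primary objective in both Part A and Part B. What is at stake is whether the reported rates of severe reactions reflect severity data that the trial already plans to collect.

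**Working it through.** The documents state no figure on this point, so there is none to reproduce. The check traces each type of late reaction through the planned outputs.

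| Event | Solicited table (SAP 4.2.1.1) | Unsolicited Grade 3 table (4.2.1.2, 6.2.2.3) | Maximum-grade summary (4.2.1.3) | Is the Grade 3 in an incidence-by-severity table? |
|---|---|---|---|---|
| (a) Onset Day 1-7, first Grade 3 after Day 7; unattended, non-serious, not an AESI | At Day 1-7 grade, and as ongoing at Day 7 | Excluded | Not eligible | No |
| (b) As (a), but attended, serious or an AESI | As (a) | Excluded | Included at worst grade | Yes |
| (c) Solicited-type event with onset in Days 8-28, reaching Grade 3 | Not included | Included | Only if attended, serious or an AESI | Yes |

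Two further outputs could in principle cover row (a):

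- The duration-by-grade summary would reflect Grade 3 days after Day 7 only if the reporting period extends that far. Even then it summarises days; it is not specified as a count of participants with Grade 3.
- The combined table of solicited and unsolicited AEs in SAP 4.6 specifies no grade.

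On data availability, events ongoing after Day 7 are recorded in the eCRF (SAP 4.2.1.1), and Protocol 10.3.6.3 has the investigator assess the intensity of each AE reported during the study. The SAP does not say whether the eCRF holds a daily or a maximum grade after Day 7. A maximum is all that the fix needs.

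**Scale.** Input: 83 participants per group in both parts (SAP 5). One omitted participant changes a Grade 3 row as follows (exact Clopper-Pearson intervals):

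- 0/83 = 0.0%, 95% CI 0 to 4.3%
- 1/83 = 1.2%, 95% CI 0.0 to 6.5%

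The rate of row (a) events is not documented. For assumed rates p, the chance of at least one case among n participants is 1 - (1 - p)^n:

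| Assumed p | One group, n = 83 | Part B, n = 249 | Part A, n = 415 |
|---|---|---|---|
| 0.2% | 15% | 39% | 56% |
| 0.5% | 34% | 71% | 88% |
| 1% | 57% | 92% | 99% (98.5%) |
| 2% | 81% | 99% | over 99% |

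For example, 1 - 0.995^83 = 0.34. These rates are illustrations only.

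**The case against.** A reader might infer that late severe reactions appear in no severity table at all. The documents do not support that. Rows (b) and (c) are tabulated by severity, and the exclusion in SAP 6.2.2.3 is confined to the unsolicited summary, so it does not reach SAP 4.2.1.3.

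A reader might also infer that an ongoing reaction first attended after Day 7 is lost from the MAAE endpoint, because the protocol says of medical attention: "This information will be recorded in the participant's eDiary (for solicited AEs"), and the eDiary covers Days 1-7. That is not shown either. The MAAE definition (Protocol 10.3.5) covers any AE leading to a medical visit and does not exclude solicited events. MAAEs are collected to study end, and solicited events ongoing after Day 7 are in the eCRF, where medical attention is recorded as part of normal AE reporting. The route for this case is not spelled out, but an unstated route is not a demonstrated loss.

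Nor do the documents show that the review committees lack the information. The IDMC reviews all available safety data (Protocol 8.5.1), and the outputs supporting IDMC and SRT reviews are specified in a separate document (SAP 4.5.1).

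It is also fair to say that the Day 1-7 table matches the primary endpoint as defined, that the affected case must meet several conditions at once, and that 1/83 is simply the weight of any one participant.

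All of this stands, and it narrows the point to row (a). It does not remove row (a): there the stated counting rules, and not merely missing detail, keep the peak grade out of every incidence table.

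**Conclusion.** The concern holds in a narrow form. A solicited reaction with onset in Days 1-7 that first reaches Grade 3 after Day 7, and is not medically attended, serious or an AESI, has its Grade 3 shown only in a flagged listing and possibly in the duration-by-grade summary.

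The frequency is undocumented and probably low; each such participant is 1.2% of an arm. The conclusion assumes that the exclusion in SAP 6.2.2.3 applies to the Grade 3 unsolicited table as well as the overall one, which is its natural reading because SAP 4.2.1.2 makes the Grade 3 table a similar tabulation of the same events. The primary Day 1-7 analysis is not in error. This is an inexpensive improvement to safety reporting.

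**What to change.** Keep the Day 1-7 solicited tables and the rule against double counting. Then:

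1. Add to SAP 4.2.1.1 one supplementary table by group, for solicited events with onset in Days 1-7, of maximum grade over the whole event (to resolution or data cut). Use eDiary grades to Day 7 and the eCRF intensity thereafter.
2. Define the reporting period for the duration-by-grade summary in SAP 4.2.1.1, stating whether it extends past Day 7.
3. Optional clarification: confirm that medical attention first sought after Day 7 for an ongoing solicited event is recorded in the eCRF and counted as an MAAE.

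The cost is one table and a few sentences, with no new visits or samples. The downside for the sponsor is that reported Grade 3 rates may be slightly higher.

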### **6.2.3. Display of Decimals**

#### **6.2.3.1. Percentages**

Percentages and their corresponding confidence limits will be displayed with 1 decimal except for 100%, in which case no decimal will be displayed.

#### **6.2.3.2. Differences in Percentages**

Differences in percentages and their corresponding confidence limits will be displayed with 2 decimals.

#### **6.2.3.3. Demographic/Baseline Characteristics Statistics**

The mean, median, and standard deviation for continuous baseline characteristics (height, weight, BMI, pre-dose body temperature) will be presented with 1 decimal.

The minimum and maximum values and quartile values (if required) will be presented with the same number of decimals as the observed values.

The maxima and minima of transformed height/weight variables will be displayed without decimals.

The maximum and minimum of transformed body temperatures will be displayed with 1 decimal.

#### **6.2.3.4. Serological Summary Statistics**

CCI

CCI

CCI

CCI

#### 6.2.4. Trademarks

Trademarks of the GlaxoSmithKline /Group of Companies	Trademarks not owned by the GlaxoSmithKline Group of Companies
Not applicable	SAS
Not applicable	CCI

